# Tumor Markers

Tumor markers alone cannot be used to assess response. If markers are initially above the upper normal limit, they must normalize for a patient to be considered in complete clinical response. Specific guidelines for both CA-125 response (in recurrent ovarian cancer) and PSA response (in recurrent prostate cancer) have been published [*JNCI* 96:487-488, 2004; *J Clin Oncol* 17, 3461-3467, 1999; *J Clin Oncol* 26:1148-1159, 2008]. In addition, the Gynecologic Cancer Intergroup has developed CA-125 progression criteria which are to be integrated with objective tumor assessment for use in first-line trials in ovarian cancer [*JNCI* 92:1534-1535, 2000].

# Cytology, Histology

These techniques can be used to differentiate between partial responses (PR) and complete responses (CR) in rare cases (e.g.,

residual lesions in tumor types, such as germ cell tumors, where known residual benign tumors can remain).

The cytological confirmation of the neoplastic origin of any effusion that appears or worsens during treatment when the measurable tumor has met criteria for response or stable disease is mandatory to differentiate between response or stable disease (an effusion may be a side effect of the treatment) and progressive disease.

FDG-PET

FDG-PET may not be used as a response assessment in this study.

# 6.1.4 **Response Criteria**

6.1.4.1 Evaluation of Target Lesions

# Complete Response (CR)

Disappearance of all target lesions. Any pathological lymph nodes (whether target or non-target) must have reduction in short axis to < 10 mm.

# Partial Response (PR)

At least a 30% decrease in the sum of the diameters of target lesions, taking as reference the baseline sum diameters.

# Progressive Disease (PD)

At least a 20% increase in the sum of the diameters of target lesions, taking as reference the smallest sum on study (this includes the baseline sum if that is the smallest on study). In addition to the relative increase of 20%, the sum must also demonstrate an absolute increase of at least 5 mm. (Note: the appearance of one or more new lesions is also considered progression, See Section 6.1.4.3).

# Stable Disease (SD)

Neither sufficient shrinkage to qualify for PR nor sufficient increase to qualify for PD, taking as reference the smallest sum diameters while on study. (Note: a change of 20% or less that does not increase the sum of the diameters by 5 mm or more is coded as stable disease)

To be assigned a status of stable disease, measurements must have met the stable disease criteria at least once after study entry at a minimum interval of eight weeks.

# 6.1.4.2 Evaluation of Non-Target Lesions

# Complete Response (CR)

Disappearance of all non-target lesions and normalization of tumor marker level. All lymph nodes must be nonpathological in size (< 10 mm short axis) **NOTE:** If tumor markers are initially above the upper normal limit, they must normalize for a patient to be considered in complete clinical response.

#### Non-CR/Non-PD

Persistence of one or more non-target lesion(s) and/or maintenance of tumor marker level above the normal limits.

#### Progressive Disease (PD)

Appearance of one or more new lesions and/or *unequivocal progression* of existing non-target lesions (see Section 6.1.4.3). *Unequivocal progression* should not normally trump target lesion status. It must be representative of overall disease status change, not a single lesion increase.

When the patient also has measurable disease, there must be an overall level of substantial worsening in non-target disease such that, even in the presence of SD or PR in target disease, the overall tumor burden has increased sufficiently to merit discontinuation of therapy. A modest "increase" in the size of one or more on-target lesions is usually not sufficient to qualify for unequivocal progression status. The designation of overall progression solely on the basis of change in non-target disease in the face of SD or PR of target disease will therefore be extremely rare.

When the patient only has non-measurable disease, the increase in overall disease burden should be comparable in magnitude to the increase that would be required to declare PD for measurable disease: i.e., an increase in tumor burden from "trace" to "large", an increase in nodal disease from "localized" to "widespread", or an increase sufficient to require a change in therapy.

Although a clear progression of "non-target" lesions only is exceptional, the opinion of the treating physician should prevail in such circumstances, and the progression status should be confirmed at a later time by the review panel (or Principal Investigator).

6.1.4.3 Evaluation of New Lesions

The appearance of new lesions constitutes Progressive Disease (PD).

# 6.1.4.4 Evaluation of Best Overall Response

The best overall response is the best response recorded from the start of the treatment until disease progression/recurrence or non-protocol therapy (taking as reference for progressive disease the smallest measurements recorded since the treatment started). The patient's best response assignment will depend on the achievement of both measurement and confirmation criteria.

Target Lesions	Non-Target Lesions	New Lesions*	Best Overall Response	Remarks
CR	CR	No	CR	
CR	Non-CR/Non-PD	No	PR	
CR	Not evaluated	No	PR	
PR	Non-PD/not evaluated	No	PR	
SD	Non-PD/not evaluated	No	SD	Documented at least once ≥ 8 wks. from study entry
PD	Any	Yes or No	PD	
Any	PD**	Yes or No	PD	No prior SD, PR or CR
Any	Any	Yes	PD	

#### For Patients with Measurable Disease (i.e., Target Disease)

\*See RECIST 1.1 manuscript for further details on what is evidence of a new lesion.

\*\*In exceptional circumstances, unequivocal progression in non-target lesions may be accepted as disease progression.

**NOTE:** Patients with a global deterioration of health status requiring discontinuation of treatment without objective evidence of disease progression at that time should be reported as "*symptomatic deterioration*." Every effort should be made to document the objective progression even after discontinuation of treatment.

# **Duration of Response**

# **Duration of Overall Response**

The duration of overall response is measured from the time measurement criteria are met for CR or PR (whichever is first recorded) until the first date that recurrent or progressive disease is objectively documented (taking as reference for progressive disease the smallest measurements recorded since the treatment started).

The duration of overall CR is measured from the time measurement criteria are first met for CR until the first date that progressive disease is objectively documented.

#### **Duration of Stable Disease**

Stable disease is measured from the start of the treatment until the criteria for progression are met, taking as reference the smallest measurements recorded since the treatment started, including the baseline measurements.

To be assigned a status of stable disease, measurements must have met the stable disease criteria at least once after study entry at a minimum interval of eight weeks.

# Rev. 6/15 **7.** Study Parameters

#### 7.1 Therapeutic Parameters

- 1. Prestudy scans and x-rays used to assess all measurable or non-measurable sites of disease must be done within **4 weeks** prior to randomization/registration.
- 2. Prestudy CBC (with differential and platelet count) should be done ≤ **4 weeks** before randomization/ registration.
- All required prestudy chemistries, as outlined in Section 3, should be done ≤ 4 weeks before randomization/registration – unless specifically required on Day 1 as per protocol.

	Test / Assessment	Pre- Study	Every 2 weeks	Every 4 weeks	Every 6 weeks	Every 8 weeks until progression	Follow- up 
	Physical						
	History and Physical	Х	Х				Х
	Weight and Performance Status	Х	Х				
	Blood Pressure 	х	Х				
	Toxicity Assessment	Х	X 	X 			
	Disease Assessment	Х					
	EKG	Х					X 
	Laboratory						
	CBC/diff/plts	X 	Х				
	Chemistry Panel (chem. 6 including creatinine)	x	х				
	Calcium	Х		Х			
Rev. 6/14	Albumin	Х		Х			
	Magnesium	Х	Х				
	Liver Panel (AST/ALT/Bilirubin)	Х	Х				
Rev. 11/14	Urine Protein 	Х			Х		
	Blood or Urine Pregnancy Test 	Х			Х		X9
	K-ras mutation Status	Х					
Rev. 12/14	PT/INR	X 					
	RADIOLOGIC EVALUATION						
	CT scans (chest/abd/pelvis)	Х				X4	Х
	Pathology Submissions 	Х					

1. Every 3 months if patient is < 2 years from study entry, every 6 months if patient is 2-5 years from study entry. No specific requirements if patient is more than 5 years from study entry.

2. CBCs (with differential and platelet count) which includes WBC, ANC, Platelets, Hbg, and Hct required for protocol therapy must be done < 24 hours prior to the treatment cycle.

3. Within 2 weeks prior to registration for women of childbearing potential; and every 6 weeks during treatment or per institutional guidelines, whichever is shorter.

4. CT scans every 4 cycles until progression.

- 5. At the end of treatment. Repeat as clinically indicated.
- Rev. 12/14 6. Toxicity Assessment every 2 weeks for the first 4 cycles on study and then every 2 cycles thereafter. An assessment is also required at the end of treatment and 30 days after the end of treatment.
  - 7. Blood pressure should be monitored twice per week for the first 4 weeks and then every 2 weeks thereafter.
- Rev. 11/14 8. UPC or urine protein on dipstick or routine urinalysis (UA). However, in the occurrence of 2+ urine protein on dipstick or UA or a UPC  $\geq$  0.5, a 24-hour urine collection for protein must be obtained.
  - 9. At the end of treatment with a 30 day safety followup. Repeat as clinically indicated.
- Rev. 12/14 10. International Normalized Ratio (INR) ≤ 1.6 (unless receiving anticoagulation therapy). Patients on full dose anticoagulation must be on a stable dose (minimum duration 14 days) of oral anticoagulant or low molecular weight heparin. If receiving warfarin, the patient must have an INR ≤ 3.0 and no active bleeding (i.e., no bleeding within 14 days prior to first dose of study therapy).
  - 11. Submit from patients who consent "Yes" to "May your coded samples and related coded information be kept for use in research to learn about, prevent, find or treat cancer?" See Section 10.

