						dose of ramucirumab is to be recalculated should atients weight change by 10% or more.
				5.1.3.2	Cetuxim	ab 400 mg/m² IV q 14 days
						first infusion is to be administered over 120 tes with subsequent infusions over 60 minutes.
				5.1.3.3	Irinoteca	n 150 mg/m² IV over 60-90 minutes q 14 days
						umab should be given first, followed by cetuximab i irinotecan.
					Repeat of	cycles every 14 days until progression.
					NOTE:	It is recommended that 50mg of diphenhydramine be administered prior to the initial 3 doses of ramucirumab, and may or may not be continued for subsequent doses per the investigator's discretion.
					NOTE:	Irinotecan pre-medication should be given per standard institutional practice.
Rev. 12/11, 0	6/14	5.2	Adverse E	vent Repor	ting Requ	iirements
				_		

5.2.1 **Purpose** 

Adverse event (AE) data collection and reporting, which are required as part of every clinical trial, are done to ensure the safety of the patients enrolled, as well as those who will enroll in future studies using similar agents.

- **Routine reporting:** Adverse events are reported in a routine manner at scheduled times during a trial (please refer to the E7208 Forms Packet for the list of forms with directions and timeframes for routine adverse event reporting).
- **Expedited reporting**: In addition to routine reporting, certain adverse events must be reported in an expedited manner via CTEP-AERS for timelier monitoring of patient safety and care. The following sections provide information and instructions regarding expedited adverse event reporting.

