# 5.4.1 General Considerations

- a. A new cycle of treatment may begin when the ANC is ≥ 1,500/mcl, the platelet count is ≥ 75,000/mcl, and any treatment-related GI toxicity is resolved to ≤ Grade 1.
- b. If the initiation of a new cycle, or treatment during a cycle is delayed for ≥ 4 weeks, the patient should be removed from protocol treatment.
- c. Held doses are not to be made up.
- d. If one therapeutic agent is permanently discontinued secondary to toxicity, then therapy with the other study agents should continue and the patient should remain on-study with full adherence to all protocol-related requirements
- e. In the event of serious or life-threatening conditions, hold the offending agent. If the patient is to continue on therapy, all agents should be held until the toxicity resolves to grade < 2.

ARM	AGENT	INITIAL DOSE	LEVEL -1	LEVEL -2	
	Cetuximab	500 mg/m 	400 mg/m 	250 mg/m 	
A (IC)	Irinotecan	180 mg/m 	150 mg/m 	120 mg/m 	
B (ICR) Closed to accrual	Ramucirumab	8 mg/kg	6 mg/kg	5 mg/kg	
	Cetuximab	500 mg/m 	400 mg/m 	250 mg/m 	
	Irinotecan	180 mg/m 	150 mg/m 	120 mg/m 	
	Ramucirumab	6 mg/kg	5 mg/kg	4 mg/kg	
C (mICR)	Cetuximab	400 mg/m 	250 mg/m 	200 mg/m 	
	Irinotecan	150 mg/m 	120 mg/m 	90 mg/m 	

f. Dose reductions for all agents are as follows:

**NOTE:** In the event that an agent is given at dose level (-2) and dose modification rules call for further reduction, the agent should be discontinued.

Rev. 12/11, 6/14

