# 5.4.8 Hypertension (Dose delays for Ramucirumab only)

Treat with anti-hypertensive medication as needed. The goal of BP control should be consistent with general medical practice Consider increased BP monitoring; Grade 1 start anti-hypertensive medication if (SBP 120-139 mmHg or DBP 80-89 mm Hg) appropriate Grade 2 asymptomatic Begin anti-hypertensive therapy and continue agent (SBP 140-159 mmHg or DBP 90-99 mm Hg) Grade 2 symptomatic Start or adjust anti-hypertensive (SBP 140-160 mmHg or DBP 90-100 mm Hg) medication • Grade 3 Hold agent until symptoms resolve AND BP < 160/90mmHg  $(\geq$  SBP 160 mmHg or  $\geq$  DBP 100 mmHg • Grade 4 Discontinue agent (Hypertensive crisis or malignant hypertension)

Patients who hold or discontinue Ramucirumab due to hypertension may continue other protocol treatment.

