# 6. Measurement of Effect

6.1 Antitumor Effect – Solid Tumors

For the purposes of this study, patients should be re-evaluated for response every eight weeks.

Response and progression will be evaluated in this study using the international criteria proposed by the revised Response Evaluation Criteria in Solid Tumors (RECIST) guideline (version 1.1) [*Eur J Ca* 45:228-247, 2009]. Changes in the largest diameter (unidimensional measurement) of the tumor lesions and the shortest diameter in the case of malignant lymph nodes are used in RECIST.

- The following general principles must be followed:
  - 1. To assess objective response, it is necessary to estimate the overall tumor burden at baseline to which subsequent measurements will be compared. All baseline evaluations should be performed as closely as possible to the beginning of treatment and **never more than four weeks** before registration.
  - 2. Measurable disease is defined by the presence of at least one measurable lesion.
  - 3. All measurements should be recorded in metric notation by use of a ruler or calipers.
  - 4. The same method of assessment and the same technique must be used to characterize each identified lesion at baseline and during follow-up.

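### The CT scans that date PFS run on unreconciled clocks: every 8 weeks, every 4 cycles, and every 3 months in the Follow-up column

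*Combined protocol and SAP*

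**What the plan says.** Section 6.1 sets the general rule: "patients should be re-evaluated for response every eight weeks". In the Section 7.1 table, the on-study CT mark sits under the heading "Every 8 weeks until progression". Footnote 4 to that mark reads "CT scans every 4 cycles until progression". The CT row has a further mark under Follow-up, and footnote 1 sets that column at 3-month intervals up to 2 years from study entry and 6-month intervals from 2 to 5 years.

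Section 5.1 plans "cycles every 14 days until progression" in both open arms. Section 5.4.1a makes the start of each cycle conditional on recovery: "A new cycle of treatment may begin when the ANC is ≥ 1,500/mcl", with matching conditions for platelets and GI toxicity. Section 5.4.1b removes a patient from protocol treatment only at a longer delay: "If the initiation of a new cycle, or treatment during a cycle is delayed for ≥ 4 weeks". Shorter delays are therefore permitted.

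Section 5.7 requires follow-up for response until progression, including after early discontinuation or a switch to other therapy, but gives no interval. Section 9.1 makes PFS the primary endpoint, counts deaths without prior progression as events, and tests it with a one-sided stratified log-rank test at 15%. No section says which clock governs the scans, and no scan window is given.

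**The concern.** A calendar rule and a cycle rule coincide only while treatment runs on time. Once a cycle is delayed, the calendar scan stays put and the cycle-counted scan moves with treatment. The date on which progression can be found then depends on tolerability, and tolerability may differ between an arm with ramucirumab and one without.

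If sites follow the footnote and one arm has more delay, that arm's progressions are dated later with no difference in disease course. More delay in Arm C would make the test anti-conservative; more delay in Arm A would work against Arm C.

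A related gap opens when a patient stops treatment without progression. There are no cycles left to count, the column heading still implies 8 weeks, and the Follow-up column implies 3 months. If such patients are more common in one arm, the choice of interval matters there too.

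**Working it through.** **The clocks side by side** (d = total delay in weeks over four cycles)

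| Source | Undelayed | With delay d | Off treatment, no progression |
|---|---|---|---|
| Section 6.1 | 8 weeks | 8 weeks | 8 weeks implied |
| Section 7.1, column heading | 8 weeks | 8 weeks | 8 weeks implied |
| Section 7.1, footnote 4 | 4 × 14 = 56 days = 8 weeks | 8 + d weeks | no date |
| Section 7.1, Follow-up column and footnote 1 | – | – | 3 months (52/4 = 13 weeks) in years 0–2 |
| Section 5.7 | – | – | until progression, no interval |

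For d = 1 or 2 the footnote gives 9 or 10 weeks. A single delay just short of the 4-week limit gives 8 + (just under 4), that is, just under 12 weeks.

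**The plan's own figure.** Section 9.1 states over 85% power with 67 events for medians of 4.5 and 7.65 months at one-sided 15%. The ratio of medians is 7.65/4.5 = 1.7, so HR = 0.588.

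- Schoenfeld: Φ(√67/2 × ln 1.7 − 1.036) = Φ(2.172 − 1.036) = 87.2%.
- Freedman: Φ(√67 × 0.412/1.588 − 1.036) = Φ(2.122 − 1.036) = 86.1%.

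The stated power reproduces. It takes no account of scan timing.

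**Illustrative size.** The false-positive rate was simulated with no true difference between arms.

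- *From the documents:* 48 per arm, exponential PFS with median 4.5 months (here in both arms), accrual over 10 months, analysis at the 67th event, one-sided 15%.
- *Assumed:* each cycle has probability p of a one-week delay, so the gap is 8 + Binomial(4, p) weeks, mean 8 + 4p, for patients scanned by the footnote and 8 weeks for the rest. Scan days vary with SD 1 or 2 weeks. Either all or half of patients are scanned by the footnote. 25% of events are dated exactly and the rest at the next scan. Non-events are censored at the last scan.
- *Simplified:* unstratified test, no interim look.

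There were 20,000 trials per scenario, so SE = √(0.15 × 0.85/20,000) = 0.25 points.

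| Delay per cycle, A / C | Mean gap, A / C (weeks) | SD 1, all | SD 1, half | SD 2, all | SD 2, half |
|---|---|---|---|---|---|
| 5% / 7% | 8.20 / 8.28 | 15.96% | 15.24% | 15.07% | 15.21% |
| 3% / 10% | 8.12 / 8.40 | 17.18% | 15.80% | 15.84% | 15.52% |
| 3% / 17% | 8.12 / 8.68 | 18.52% | 16.89% | 16.34% | 15.89% |

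- *Controls (SD 1 / SD 2):* no delay, 14.98% / 15.26%; equal 10% delays, 15.26% / 15.38%.
- *Extreme case:* 3% / 17%, all on the footnote and every event dated by scan, 20.47% (SD 1) and 16.94% (SD 2).
- *Separately coded repeat* (4,000 trials, SE about 0.6 points): 14.9% with no delay, 17.6% for 3% / 17% with SD 1, and 21.7% for the same with every event dated by scan.

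In the mildest scenario, three of the four results cannot be told apart from the controls. The simulation does not cover the 3-month Follow-up interval.

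**The case against.** The best reply is that the documents largely settle the matter. Section 6.1 governs measurement of effect and uses the calendar, and so does the heading over the CT cell. Footnote 4 is the only cycle-based wording for scans, and cycles stand in for weeks elsewhere: footnote 6 explains marks in weekly columns by counting cycles, and the reorder instructions in Section 8.3.9 equate three cycles with six weeks. This stands as far as it goes, and the footnote is probably shorthand. But a footnote normally qualifies its cell, and a site has no rule telling it to ignore this one.

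The second reply is that cycles may slip less than Section 5.4.1a suggests. Section 5.4.2 continues both antibodies when irinotecan is held for blood counts. Sections 5.4.3 to 5.4.5 avoid ramucirumab delay for diarrhea, for nausea and vomiting, and for grade 2–3 mucositis. Because only Arm C has ramucirumab, counting any dosing visit as a cycle could even make Arm C slip less. Against this, the grade 3 diarrhea row stops further treatment until improvement, and grade 4 mucositis holds everything. These rules sit in tension with Section 5.4.1a and need reconciling; until then, neither the frequency nor the direction of delay by arm is known.

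Three stronger readings are tempting and not supported.

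- *Arm B's experience shows that Arm C will be delayed more.* Section 1.6 reports dose reductions in 15/16 Arm B against 3/17 Arm A patients, and 65% against 99% irinotecan dose intensity. Those figures mix reductions, holds and delays, and "Held doses are not to be made up", so they cannot be read as cycle delay. Arm C also starts at lower doses under stricter eligibility.
- *Arm B's exits show more off-treatment patients without progression.* Section 1.6 reports that 1 of 5 Arm B exits was for progression, against 8 of 9 in Arm A. The numbers are small, and the other four may include the two toxic deaths.
- *The error rate is 25% to 34%.* A cruder calculation, with exact scan dates, delay only in Arm C and every event dated by scan, gives 24.7% to 33.6%. It already gives 16.5% with no delay and does not rise steadily with delay (27.5% at one extra week, 24.7% at two), so it is no guide to size.

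**Conclusion.** The conflict in the text is certain; its effect on the trial is conditional. This is a minor to moderate point. Distortion needs both that some sites scan by cycle and that cycle delay differs by arm. The documents show neither, and if either fails there is no inflation from this source.

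Under the assumed inputs the nominal 15% test runs at about 15% to 18.5% when Arm C is delayed more. It reaches 20% to 22% only with a large delay imbalance, tight scan days, all patients on the footnote and every event dated by scan. That last condition is unlikely, since PFS includes deaths. A reader might infer that the trial's type I error is inflated in favor of Arm C; the documents support only the possibility. The point still merits action because it concerns the dating of the primary endpoint and the correction is nearly free.

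**What to change.** 1. Reword footnote 4 to match Section 6.1: CT every 8 weeks by calendar from randomization, in both arms, until progression, regardless of cycle delays or held agents.
2. Reconcile the Follow-up column CT mark and footnote 1 with Section 5.7, so that patients who stop treatment without progression have one stated interval, the same in both arms. Editing footnote 4 alone leaves this gap open.
3. At analysis, tabulate actual scan intervals by arm, since some patients may already have been scanned by cycle.
4. Optionally, add an assessment-timing sensitivity analysis of PFS, such as an interval-censored log-rank test. In 8,000 simulated trials (SE about 0.4 points) of the 3% / 17% case with SD 1 week, it gave 14.7% against 17.9% for the standard test. With every event dated by scan it gave 17.9% against 20.7%. It removes only part of the distortion there, so the wording change comes first.

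Cost: two small table edits, one table and, if wanted, one extra analysis. There may be a few more scans after treatment stops, because Section 5.7 requires follow-up to progression without fixing how often.
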